6.1 Timing of Analyses

The final analysis will be performed after 340 patients have been included.

6.2 Analysis Populations

6.2.1 Full Analysis Population

All participants who were randomized.

6.2.2 Per Protocol Population

All participants who received a SVP.

6.2.3 Intention to treat Population

Analyses will be performed on all participants in the original assigned randomized group.

6.3 Missing Data

Missing data are assumed of missing at random (MAR). Less than 10 % of data are assumed missing. Missing data will be quantified and reported.

6.4 Interim Analyses and Data Monitoring

Interim analyses are not expected to lead to early closure of neither randomization on safety nor efficacy grounds. Both techniques are established and clinically approved methods and complications are very uncommon. After 100 respectively 200 patients analyses of adverse events (AE) will be performed in which we expect a frequency lower than 15% based on previous studies (PACSPI1). In the event of a higher frequency the sponsor will discuss further action with the monitor.

6.4.1 Documentation of Interim Analyses

Snapshots of the data available at each interim analysis will be preserved. Reports of AE analyses will be stored in the sponsor's documents enabling recreating the decision process from the trial archive.

6.5 Multi-centre Studies

This trial will be carried out in the following anaesthesia departments:

OP/IVA-kliniken, Ryhov County Hospital, Sweden

AnOpIVA-kliniken, Linköping University Hospital, Sweden

Co-investigators at participating sites will have access to REDCap. Centres are provided with the PCS pump. There will be no restrictions in the choice of LA-solution being left up to local practice at participating sites

6.6 Demographic and Baseline Variables

Gender, age, American Society of Anesthesiologists (ASA)-class, BMI, cancer type, treatment strategy, preoperative analgesia, procedural time, sedation score at timepoints T1-4 (OAAS), sedation volym, alfentanil (mg) delivered, propofol (mg) delivered will be reported for demographic and interventional data.

7 Statistical Analyses

The analysis will be produced on intention to treat population.

Data will be summarised by treatment group. Summary statistics of demographic and baseline variables will be reported. All continuous variables will be summarised using the following descriptive statistics: n (non-missing sample size), median, interquartile range. The frequency and percentages (based on the non-missing sample size) of observed levels will be reported for all categorical measures. Categorical data will be analysed with Chi2 test, continuous data will be analysed with Mann-Whitney U test.

Repeated measurement of analysis of variance is used for the analysis of treatment effect of PCS on QoR-15 scores. This model takes the inter- and intra-individual variation into account and provides flexibility in handling missing data which will be reported. Fixed factors include treatment group, time and treatment-by time-interaction. Confidence intervals will be reported and adjustment for planned comparison conducted. Testing will be two-sided with a 5% significance level.

Demographic and baseline data will be listed by treatment group in a table.

Primary endpoint will be displayed in a figure.

Secondary endpoints will be displayed in a figure.

8 Reporting Conventions

P-values ≥ 0.01 will be reported to two decimal places, p-values ≥ 0.001 will be reported to three decimal places; p-values less than 0.001 will be reported as “ <0.001 ”. The median and any other statistics other than quantiles, will be reported to one decimal place greater than the original data.

9 Technical Details

Analyses will be carried out with the study statistician. Analyses will be carried out in SPSS, IBM

References

<http://dx.doi.org/10.1093/bja/aev413>.
<http://dx.doi.org/10.1097/ALN.0b013e318289b84b>.

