Considering a minimal clinically important difference (MCID) of 6 that has been suggested to constitute a meaningful change in health status with a standard deviation of 19 a total number of 314 patients is needed to detect this change with 80% power, 2-sided, at a significance level of 5%.

6 General Considerations

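### Protocol section 7 names repeated-measures ANOVA for QoR-15 but credits it with a missing-data flexibility that belongs to a mixed model, and does not say which contrast is primary

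*Protocol*

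**What the plan says.** The Protocol is the plan for the QoR-15 sub-study. The total score is taken three times: before surgery, in PACU before discharge, and at 24 h by telephone.

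- **Method (section 7):** "Repeated measurement of analysis of variance is used for the analysis of treatment effect of PCS on QoR-15 scores".
- **Property claimed for it (section 7):** "This model takes the inter- and intra-individual variation into account and provides flexibility in handling missing data which will be reported".
- **Terms (section 7):** "Fixed factors include treatment group, time and treatment-by time-interaction". No random effect, covariance structure, estimation method or primary contrast is given.
- **Software (section 9):** "Analyses will be carried out in SPSS, IBM". The procedure is not named.
- **Missing data (section 6.3):** "Missing data are assumed of missing at random (MAR). Less than 10 % of data are assumed missing". The unit of the 10% (patient, score or item) is not stated, and no imputation is named.
- **Population (sections 6.2.3 and 7):** intention to treat, with all participants in the arm they were randomised to.
- **Sample size (section 5):** for a 6-point difference and SD 19, "a total number of 314 patients is needed to detect this change with 80% power"; 340 are planned.

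The parent SAP does not settle the matter. Its section 6.5 names an imputation method without defining it, and its section 18 leaves QoR-15 to a separate manuscript.

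**The concern.** Two different analyses fit section 7. Classical repeated-measures ANOVA (in SPSS, the repeated-measures option of the general linear model) needs a complete set of scores and deletes any patient who lacks one. A linear mixed model fitted by likelihood uses every observed score and is valid under missing at random. The name points to the first and the described property to the second.

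The choice affects who is analysed. Under deletion, a patient with baseline and PACU scores but no telephone score drops out of an analysis described as intention to treat. The complete-case estimate can also be biased when missingness depends on an observed score. The two methods can give different estimates and p-values for the primary endpoint, so the choice should be fixed before the data are seen.

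The second issue is baseline. Because the preoperative score is one of three levels of time, the treatment main effect averages in a score that treatment cannot influence. The primary endpoint in section 3.2 concerns change between groups at the time points, but section 7 does not say which term or comparison answers it.

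**Working it through.** **Inputs.** Difference 6, SD 19, two-sided 5%, 80% power, 314 needed (section 5); 340 planned, 1:1 (sections 4.1 and 5); under 10% missing (section 6.3). The within-patient correlation ρ is not given; 0.3, 0.5 and 0.7 are assumed.

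**1. The plan's own figure.** Total N = 4 × [19 × (1.960 + 0.842) / 6]² = 314.8. This agrees with 314, so the calculation is a two-sample comparison of one score.

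**2. Power if incomplete patients are deleted.** Power = Φ(6 / (19 × √(4/N)) − 1.960). The last column uses the noncentral t distribution.

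| Assumption | Complete patients | Normal | t |
|---|---|---|---|
| None missing | 340 | 82.9% | 82.7% |
| The plan's N | 314 | 79.9% | 79.7% |
| 10% of patients incomplete | 340 × 0.9 = 306 | 78.9% | 78.6% |
| 10% missing independently at two postoperative scores | 340 × 0.9² = 275 | 74.5% | 74.2% |
| 10% missing independently at all three scores | 340 × 0.9³ = 248 | 70.1% | 69.7% |

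For 306: 19 × √(4/306) = 2.172; 6/2.172 = 2.762; 2.762 − 1.960 = 0.802; Φ = 78.9%. About 7.5% of patients can be incomplete before fewer than 314 remain (1 − 314/340 = 0.076).

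**3. Deletion against a mixed model on the group-by-time test.** This is a 2-df test with SD 19 per score, compound symmetry, and 6 points at both PACU and 24 h.

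| Missing | ρ | Mixed model | Complete cases |
|---|---|---|---|
| 10% at 24 h only | 0.3 | 71.2% | 67.3% |
| | 0.5 | 85.4% | 82.2% |
| | 0.7 | 97.7% | 96.6% |
| 10% at each score | 0.3 | 66.2% | 57.5% |
| | 0.5 | 80.8% | 73.1% |
| | 0.7 | 95.9% | 92.3% |

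**4. Bias.** In simulation with about 9% missing and modest dependence on observed scores, complete-case analysis moved a true 6.0-point difference to about 5.8 to 5.9. It could be larger if the dependence differs between arms.

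**5. Baseline in the main effect.** With no difference at baseline and 6 points at each later time, the main effect is (0 + 6 + 6)/3 = 4. The SD of a three-score mean is 19 × √((1 + 2ρ)/3) = 13.88, 15.51 and 16.99 at ρ = 0.3, 0.5 and 0.7. At N = 340 the power is Φ(4 / (SD × √(4/340)) − 1.960) = 76%, 66% and 58%. For the mean of the two postoperative scores the SD is 19 × √((1 + ρ)/2), the effect is 6, and the power is 95%, 92% and 88%.

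**6. Adjusting for baseline.** If 19 is the SD of a single score, the adjusted SD is 19 × √(1 − ρ²) = 18.12, 16.45 and 13.57, and the SD of change is 19 × √(2(1 − ρ)) = 22.48, 19.00 and 14.72.

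| ρ | Change, N = 340 | Adjusted, N = 340 | Adjusted, N = 306 |
|---|---|---|---|
| 0.3 | 69% | 86% | 82.5% |
| 0.5 | 83% | 92% | 89% |
| 0.7 | 96% | 98% | 97% |

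These are for one contrast at the 5% level.

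**The case against.** A reader might infer that patients will certainly be dropped and that the trial will miss 80% power. The documents support neither.

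- **Deletion is inferred from the name.** Fixed factors, variation between and within individuals, and tolerance of missing scores are how one describes a mixed model. With the intention-to-treat and missing-at-random statements, a loosely named mixed model is the more coherent reading. This stands, but it leaves an ambiguity that needs resolving.
- **The planned 340 absorb most of the loss.** The plan's 10% is a ceiling. Two of the three scores are taken on site and only the 24 h score depends on a telephone call; with 10% missing there alone, 306 remain. This stands. The figures of 70% to 74% need missingness separately at three or two scores, which no section states.
- **The two-sample figure is not the power of the repeated-measures test.** Correct. On the group-by-time test the unknown correlation moves power more than deletion does at the stated rate.
- **Deletion need not bias the comparison between arms.** Correct. If missingness depends on baseline in the same way in both arms, and the effect does not vary with baseline, the complete-case difference is unbiased.
- **The interaction term already addresses change between groups.** It is in the model and avoids the dilution. However, the plan does not designate it, and an overall interaction test does not itself give the difference at PACU or at 24 h.
- **A covariate-adjusted model can also drop patients.** SPSS excludes those without a baseline score if baseline is a covariate, so the replacement must provide for them.

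**Conclusion.** The point holds as a mismatch between the method named and the property claimed, together with an undesignated primary contrast. It should be corrected before analysis.

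Its size is modest. Under the classical reading, with 10% of patients incomplete, power on the plan's own basis is about 79%, roughly 1 point below the stated 80%. The larger losses depend on an assumption about missingness that the plan does not make. Bias under missing at random is possible, and was small in the case simulated.

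The clearer gain is from baseline adjustment: at 340 patients, 86%, 92% and 98% power against 69%, 83% and 96% for change from baseline, at ρ = 0.3, 0.5 and 0.7. This assumes that SD 19 is for a single score, which the plan does not state.

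**What to change.** In section 7, replace the repeated-measures ANOVA sentence with a linear mixed model (SPSS MIXED, REML, unstructured covariance) that includes every randomised patient with at least one postoperative score. Adjust for baseline QoR-15 in one of two ways:

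- keep baseline in the outcome vector and constrain the arms to a common baseline mean, which retains patients without a baseline score; or
- use PACU and 24 h as outcomes, with treatment, time, treatment-by-time, baseline and baseline-by-time as fixed effects, and a stated simple imputation of any missing baseline.

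Name the between-group differences at PACU and 24 h, with 95% confidence intervals, as the primary contrasts. Section 7 already promises adjustment for planned comparisons without naming the method; state how it applies to these two. With a Bonferroni split (2.5% each, critical value 2.241 in place of 1.960), baseline-adjusted power per contrast at 306 patients would be about 74%, 83% and 95% at ρ = 0.3, 0.5 and 0.7.

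In section 6.3, say whether the 10% refers to patients or to scores. In section 5, say whether SD 19 is for a score or a change. Within-group comparisons for the secondary endpoints can still use all three time points.

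The cost is a few sentences of text.

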3.1 Study Objectives

This study measures postoperative outcome of cancer patients undergoing SVP implantation evaluated with QoR-15 and the influence of PCS on postoperative recovery. The study was pre-planned within 'Patient-controlled sedation in subcutaneous port implantation- a randomized controlled trial' (PACSPI-2, EUDRACT NUMBER 2021-003821-31) which assesses the efficacy of patient-controlled sedation (PCS) with alfentanil and propofol as adjunct to local anaesthesia during SVP implantation. Patients participating in the study are interviewed with QoR-15 at three different time points; preoperatively (baseline), postoperative in PACU (before discharge) and 24 hours postoperatively (by telephone). Assessment of QoR-15 scores between groups and time points are the study objectives in these analyses.

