3.2 Endpoints

Primary endpoint:

The primary endpoint is assessment of change in total QoR-15 score between groups at the time points.

Secondary endpoints:

Secondary endpoint is assessment of difference for each QoR dimension and for each of Parts A and B within and between groups.

Secondary endpoint is assessment of analgesic consumption and patient-reported postoperative pain perception between groups.

4 Study Methods

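### Baseline QoR-15 is modelled as an outcome time, not adjusted for, and no primary contrast is named: a baseline-adjusted, named contrast would gain precision at no cost

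*Protocol*

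**What the plan says.** Protocol section 3.1 sets three QoR-15 measurements (pre-operative, PACU before discharge, 24 hours by telephone) and closes: "Assessment of QoR-15 scores between groups and time points are the study objectives in these analyses". Section 3.2 defines the endpoint: "The primary endpoint is assessment of change in total QoR-15 score between groups at the time points". Neither singles out a time point.

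Section 7 specifies repeated-measures analysis of variance on the intention-to-treat population, two-sided at 5%: "Fixed factors include treatment group, time and treatment-by time-interaction". It adds: "Confidence intervals will be reported and adjustment for planned comparison conducted". The comparisons and the adjustment method are not given.

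Section 5 takes a minimal important difference of 6 points, a "meaningful change in health status with a standard deviation of 19", and concludes that "a total number of 314 patients is needed to detect this change with 80% power, 2-sided, at a significance level of 5" per cent. It does not say which test this is for, or whether 19 is the SD of a score or of a change. On numbers, "The final analysis will be performed after 340 patients have been included" (section 6.1) and "Less than 10 % of data are assumed missing" (section 6.3).

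The parent trial's SAP does not fill the gap. Its section 6.8 marks multiple testing as not applicable, and its section 18 leaves QoR-15 to a separate manuscript.

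**The concern.** Two things are left open.

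- **Precision.** Every patient gives a pre-operative QoR-15 before treatment, so any baseline difference between arms is chance. The listed model estimates separate baseline means for the two arms. Its group effect after surgery is then either a raw difference at one time, which ignores baseline, or a difference in change, which subtracts all of it. Neither is the most precise use of that score. The protocol's introduction hypothesizes that PCS leaves QoR-15 unaffected, so a narrow confidence interval is what would make the expected result informative.
- **The deciding test.** The text permits the interaction, the PACU contrast, the 24-hour contrast and, less naturally, the group main effect. Until one is named, the 80% power cannot be attached to the primary result. The trial is open to patients and staff (SAP 5.5.1) and the outcome is patient-reported, so the choice is better fixed in advance.

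**Working it through.** **Inputs from the documents:** difference 6; SD 19; two-sided 5%; 80% power; 314 calculated; 340 enrolled 1:1; missing data below 10%, so 340 × 0.9 = 306 at the limit.

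**Assumed, because the documents give no value:** correlation rho between baseline and post-operative score of 0.3, 0.5 or 0.7, and the same SD at each time. Triplets below follow that order.

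**1. The plan's own figure.** For two independent means, n per arm = 2 × (19/6)² × (1.960 + 0.842)² ≈ 157.4, so about 314 in total. The standard error is 19 × √(2/157) = 2.144, and 6/2.144 = 2.80. Noncentral-t power is 80% at 314, 83% at 340 and 79% at 306. The figure reproduces as one unadjusted two-group comparison at the full 5%.

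**2. Variance of the three contrasts at one post-operative time,** per patient, with score SD σ:

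- raw: σ²
- change from baseline: 2(1 − rho)σ²
- baseline-adjusted: (1 − rho²)σ²

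Adjusted/raw = 1 − rho² = 0.91/0.75/0.51, a reduction of 9/25/49%. Adjusted/change = (1 + rho)/2 = 0.65/0.75/0.85, a reduction of 35/25/15%. Both ratios are at most 1 for any rho from 0 to 1. The reason is general: raw fixes the slope on baseline at 0, change fixes it at 1, and adjustment estimates the best slope.

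**3. SDs under each meaning of 19.**

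- Of the score: change SD = 19√(2(1 − rho)) = 22.5/19.0/14.7; adjusted SD = 19√(1 − rho²) = 18.1/16.5/13.6.
- Of the change: score SD = 19/√(2(1 − rho)) = 16.1/19.0/24.5; adjusted SD = 15.3/16.5/17.5.

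**4. Power for 6 points at 314,** one test at 5%:

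| Contrast | 19 is SD of score | 19 is SD of change |
|---|---|---|
| Raw, one time | 80% at any rho | 91/80/58% |
| Change from baseline | 65/80/95% | 80% at any rho |
| Baseline-adjusted | 83/90/97% | 93/90/86% |

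Example (score, rho 0.5): 16.45 × √(2/157) = 1.857; 6/1.857 = 3.23; 3.23 − 1.96 = 1.27, a power of about 90%.

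The adjusted contrast has 82/89/97% (score) or 93/89/85% (change) at 306, and 86/92/98% or 95/92/88% at 340.

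**5. Two time points.** With Bonferroni (0.025 each; the method is my assumption), each unadjusted comparison has about 71% power at 314. If instead the better of PACU and 24 hours were picked after the fact, the false-positive rate depends on the adjustment (rho is here also the correlation between the two tests):

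- each at an unadjusted 5%: 9.5/9.1/8.3%
- each at 2.5%, as Bonferroni would require: 4.8/4.6/4.3%

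**The case against.** The strongest reply is that baseline is already used. It is a level of time, the endpoint is worded as change, and the group-by-time contrasts are differences in change from baseline. This is right. A reader might infer from the missing covariate that baseline is ignored or the estimate biased, and the documents support neither. Baseline goes unused only if the test is a raw group difference at one post-operative time. What remains is precision, because change is also beaten by adjustment whenever rho is below 1.

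Second, no shortfall in power is shown. One raw time point (SD 19 of the score) or one change contrast (SD 19 of the change) has 80% at 314 and 83% at 340. This also stands: a reader might conclude that 314 is wrong or the study underpowered, but the number is correct for a plain comparison. It is only unattached to a named test.

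Third, the 8–10% false-positive rate may look like a property of the plan. It is not. Section 7 promises adjustment, and under Bonferroni the rate is 4.3–4.8%. The higher figure applies only if that adjustment is not carried out. SAP 6.6.3 also has the analysts work on coded groups, and the sponsor expects no effect, so a motive to pick a significant contrast is weak. The fair criticism is that the comparisons and the method are unnamed.

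Finally, rho is assumed. The correlation may also differ between the two post-operative times, because every form asks about the last 24 hours and the perioperative period is 2–4 hours (SAP 5.1), so the PACU form overlaps the baseline form. That changes the size of the gain, not its direction.

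**Conclusion.** The point holds as a free improvement, not as an error that must be corrected. The planned analysis is valid, and its sample size is right for one unadjusted comparison. A baseline-adjusted contrast is at least as precise as either contrast that the listed model offers. Against the stated 80% at 314, it gives 83–97% or 86–93%, depending on what SD 19 means. The direction of the gain does not depend on the correlation; its size does, and it rests on assumed values from 0.3 to 0.7 with equal SDs. Separately, sections 3.2, 5 and 7 should be tied together, so that one named contrast carries both the primary conclusion and the power statement.

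**What to change.** **Section 7.** Make the primary analysis a linear mixed model (available in SPSS, the stated software) with unstructured covariance, on total QoR-15 at all three times. Include time, and treatment-by-time terms for PACU and 24 hours only, so that baseline means are constrained equal. An alternative is to model the two post-operative times with treatment, time, treatment-by-time, baseline and baseline-by-time. The last term matters if the correlations differ. With assumed correlations of 0.9 (baseline–PACU), 0.3 (baseline–24 h) and 0.3 (PACU–24 h), and SD 19 of the score, power at 24 hours at 314 is 73% with one common slope and 83% with baseline-by-time.

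**Sections 3.2 and 7.** Name one between-group contrast at one time point, tested once at two-sided 5%, with the other time point secondary. The sponsor should choose. The 24-hour recall period favours 24 hours, since a PACU form mostly covers time before treatment. If both are primary, name the multiplicity method.

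**Section 5.** State what SD 19 refers to and its source, and restate power for the chosen contrast with its assumed correlation.

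**Cost.** Wording only; no new data or patients. One time point becomes secondary. A plain covariate model drops patients with no baseline, and the equal-baseline model keeps them. With 340 patients, 10% of baselines missing and SD 19 of the score, power is 86/91/98% for the equal-baseline model against 82/89/97% for the plain one.

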4.4 Study Variables

All measured study variables are described in the PACSPI-2 study protocol accessible on clinicaltrials.gov (NCT05688384).

QoR-15swe (Quality of Recovery-15 Sweden) is measured on a numeric rating scale (NRS) from 0 to 10.

The score in the separate dimensions will be combined into a single value as expression for total QoR-15 score.

Del A

Hur har du mått de senaste 24 timmarna?

På en skala från 0 till 10, där 0 = Inte någon gång {dåligt} och 10 = hela tiden {utmärkt}

1	Kunnat andas lugnt	Inte någon gång	0	1	2	3	4	5	6	7	8	9	10	hela tiden
2	Kunnat njuta av maten	Inte någon gång	0	1	2	3	4	5	6	7	8	9	10	hela tiden
3	Känt dig utvildad	Inte någon gång	0	1	2	3	4	5	6	7	8	9	10	hela tiden
4	Kunnat sova gott	Inte någon gång	0	1	2	3	4	5	6	7	8	9	10	hela tiden
5	Kunnat sköta toalettbesök och personlig hygien utan hjälp	Inte någon gång	0	1	2	3	4	5	6	7	8	9	10	hela tiden
6	Kunnat kommunicera med anhöriga eller vänner	Inte någon gång	0	1	2	3	4	5	6	7	8	9	10	hela tiden
7	Fått stöd från sjukhuspersonal	Inte någon gång	0	1	2	3	4	5	6	7	8	9	10	hela tiden
8	Kan du utföra ditt arbete eller dina vanliga aktiviteter hemma	Inte någon gång	0	1	2	3	4	5	6	7	8	9	10	hela tiden
9	Känt dig trygg och haft kontroll över din tillvaro	Inte någon gång	0	1	2	3	4	5	6	7	8	9	10	hela tiden
10	Haft en känsla av allmänt välbefinnande	Inte någon gång	0	1	2	3	4	5	6	7	8	9	10	hela tiden

Del B

Har du känt något av följande symptom de senaste 24 timmarna?

på en skala från 10 till 0, där 10 = Inte någon gång {utmärkt} och 0 = hela tiden {dåligt}

11	Medelsvår smärta	Inte någon gång	10	9	8	7	6	5	4	3	2	1	0	hela tiden
12	Svår smärta	Inte någon gång	10	9	8	7	6	5	4	3	2	1	0	hela tiden

13	Illamående eller kräkning	Inte någon gång	10	9	8	7	6	5	4	3	2	1	0	hela tiden
14	Känt ångest eller oro	Inte någon gång	10	9	8	7	6	5	4	3	2	1	0	hela tiden
15	Känt dig ledsen eller deprimerad	Inte någon gång	10	9	8	7	6	5	4	3	2	1	0	hela tiden

Time table for measurement of variables

	Preop	Intraop	Postop	24h postop
QoR-15swe	x		x	x
Demographic	x			
Vital signs	x	x		
Procedure details		x		
Malignancy details	x			
Sedation assessment		x		
AE/SAE		x		
Analgesia		x		x
Time consumption	x	x	x	

5 Sample Size

Sample size calculation in the original trial was performed on its primary endpoint with the aim to detect a 50% reduction in pain perception as stated by the study protocol. 340 patients are included in the study with a 1:1 randomization.

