6.8 Multiple Testing

Not applicable

7 Summary of Study Data

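### The 80% power in Protocol section 5 holds for one unadjusted comparison, not for each of the adjusted comparisons that section 7 announces

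*Protocol*

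**What the plan says.** Protocol section 3.2 defines the primary endpoint as assessment of "change in total QoR-15 score between groups at the time points". QoR-15 is taken at three times: before surgery, in the PACU before discharge, and by telephone at 24 hours. No time point is named as primary.

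Protocol section 5 gives the sub-study's sample size. It sets the effect size at the MCID, 6 points, and assumes an SD of 19. Its conclusion is that "a total number of 314 patients is needed to detect this change with 80% power, 2-sided, at a significance level of 5" (percent). It does not mention multiplicity. The same section takes the number of patients from the parent trial: "340 patients are included in the study with a 1:1 randomization".

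Protocol section 7 plans a repeated-measures analysis of variance with group, time and their interaction. It then says "Confidence intervals will be reported and adjustment for planned comparison conducted". The sentence on the error level comes next: "Testing will be two-sided with a 5% significance level". It does not state the adjustment method, the comparisons in the family, or whether the primary test is a model term or a contrast at a given time.

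SAP 6.8, on multiple testing, reads in full "Not applicable". That SAP covers the parent trial. Its primary endpoint is maximal pain during the procedure, and its section 18 sends the QoR-15 results to a separate manuscript.

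**The concern.** Section 5 gives the whole two-sided 5% to one comparison. Sections 3.2 and 7 together describe at least two postoperative between-group comparisons with some adjustment. If the adjusted contrasts carry the primary conclusion, each is tested at a stricter level than the one used for 314, and power for a given contrast falls below the stated figure.

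This matters more than usual here because section 2 hypothesises that PCS leaves the QoR-15 score unaffected. A non-significant result is likely to be read as support for that, so the chance of missing a 6-point difference should be stated correctly. Leaving the method, family and primary contrast open also allows them to be chosen after the results are known.

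**Working it through.** **Inputs.** Difference 6, SD 19, two-sided 5%, 80% power and total 314 (Protocol section 5); 340 patients allocated 1:1 (section 5); less than 10% missing (section 6.3), so 340 × 0.9 = 306 as a lower case. The two postoperative contrasts, PACU and 24 h, follow from the measurement schedule. The adjustment method and the between-time correlations are assumptions, because the Protocol gives neither.

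**Step 1: reproduce 314.**
n per arm = 2 (z₁₋α/₂ + z₀.₈₀)² (SD/δ)² = 2 (1.960 + 0.842)² (19/6)² = 157.4, or 314.8 in total. Rounding up gives 316; the plan's 314 is 157 per arm.
Power = Φ(δ / [SD √(2/n)] − z₁₋α/₂). At 157 per arm, 19 √(2/157) = 2.144 and 6/2.144 = 2.798, so power = Φ(2.798 − 1.960) = 79.9%. The stated figure is right for one unadjusted comparison.

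**Step 2: equal split over two contrasts (α = 0.025, z = 2.241).** This is power for one given contrast.

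| Total N | δ/SE | Power at 0.05 | Power at 0.025 |
|---|---|---|---|
| 306 | 2.762 | 78.9% | 69.9% |
| 314 | 2.798 | 79.9% | 71.1% |
| 340 | 2.911 | 82.9% | 74.9% |

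For 80% at 0.025, n per arm = 2 (2.241 + 0.842)² (19/6)² = 190.6, that is 191 per arm or 382 in total.

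**Step 3: other rules for the same two contrasts.** These come from simulation of correlated normal test statistics, with a true difference of 6 at both times and a between-time correlation of 0.3, 0.5 or 0.7 (assumed).

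| Rule | N = 314 | N = 340 |
|---|---|---|
| Holm, a given contrast | 76-77% | 79-80% |
| Equal split, at least one contrast significant | 82-88% | 85-90% |
| Fixed sequence, second contrast | 67-71% | 71-75% |

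Under the fixed sequence the first contrast keeps the 0.05 column of step 2.

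**Step 4: if the primary test is a single model term.** Assume a 6-point difference at both postoperative times, none at baseline, SD 19 at each time, and one common correlation ρ. The group differences (0, 6, 6) deviate from their mean of 4 by (−4, 2, 2), with sum of squares 24. The group-by-time test has 2 degrees of freedom and noncentrality (n/2) × 24 / [361 (1 − ρ)]. At n = 157 this is 7.46, 10.44 and 17.40 for ρ = 0.3, 0.5 and 0.7, giving power of about 69%, 83% and 97% (large-sample chi-square). The group main effect, a mean difference of 4, has power of 72%, 63% and 55%. Section 5 was calculated for neither test, and its 80% can be too high or too low.

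**The case against.** The strongest reply is that section 7 contains no complete testing rule for section 5 to contradict. It keeps a 5% level, and the adjustment may apply only to follow-up contrasts after one model test, in which case no alpha is split for the primary test. That reading is open, and it rules out calling the stated power false. It does not rescue the 80%, because section 5 was not calculated for a model test (step 4).

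The size of the loss also depends on choices that the plan leaves open. Holm costs much less than an equal split, and if success means at least one significant contrast, power exceeds 80%. Section 5 does not say whether 19 is the SD of a raw score or of a change. If it is a raw-score SD and baseline is used as a covariate (correlation 0.5, assumed), power at 0.025 is about 84% at 314 and 87% at 340. With raw change scores and a correlation of 0.3 (assumed), it is 55% and 59%. All this stands, so the 71-75% is conditional.

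Three stronger readings are tempting, and the documents do not support them.

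- A reader might infer that 314 is an arithmetic error. It reproduces on its own inputs.
- A reader might set SAP 6.8 against Protocol section 7 as a direct contradiction, and conclude that the error rate will go uncontrolled. SAP 6.8 belongs to the parent trial and QoR-15 is reported separately, while the sub-study's own plan does announce an adjustment. This is a point to align.
- A reader might count three comparisons by including baseline. No section lists a baseline contrast as planned, and the endpoint is worded as a change.

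**Conclusion.** The point holds as a mismatch between the sample-size statement and the announced testing. The 80% at 314 belongs to one unadjusted two-group comparison. It is not supported for each adjusted comparison over the two postoperative time points, nor was it derived for a single group-by-time test.

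Under an assumed equal split, the chance of missing a true 6-point difference at a given time point is about 29% at 314, 25% at 340 and 30% at 306, against the 20% that section 5 implies. Under Holm at 340 patients the shortfall almost disappears, provided that both effects are real. These figures rest on a difference of 6, an SD of 19 applied to the quantity analysed, two contrasts, and the assumed method and correlations. The gap in the plan does not depend on them: the primary test, the family and the method are undefined, and section 5 does not allow for the announced adjustment.

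**What to change.** **Preferred.** In Protocol sections 3.2 and 7, name one primary between-group contrast in total QoR-15, tested at the full two-sided 5%. The sponsor should choose the time point before the group code is opened to the analysts; nothing in the documents ranks 24 h above PACU or the reverse. Test the other postoperative time point, also at 5%, only if the first is significant. The section 5 calculation then applies to the primary test, with about 83% power at 340 and 79% at 306. The cost is that the second claim becomes conditional on the first, with about 67-71% power at 314 and 71-75% at 340 under the step 3 assumptions. For the second time point, this is no better than an equal split.

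**Alternative.** Keep an adjustment, name its method and the comparisons it covers, and restate the power in section 5: about 71% at 314 and 75% at 340 per contrast for an equal split over two. If a model term is to be the primary test, say so and calculate power for that term with a stated correlation.

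In both cases, say in section 5 what the SD of 19 refers to, and state power at 340 with the allowance for missing data. In SAP 6.8, replace the present entry for QoR-15 with a reference to the sub-study's rule. The change takes a few sentences in two documents and no additional patients.
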